### **6.3    Secondary Endpoints – Safety**

A secondary endpoint is to evaluate the toxicity profile of pacritinib therapy in hospitalized patients with severe COVID-19 with or without cancer. In general, this will be assessed through the analysis of treatment-emergent adverse events including incidence, seriousness, relatedness to pacritinib, and severity.

#### **6.3.1    Adverse Events**

Adverse Events (AEs) will be coded using the Medical Dictionary for Regulatory Activities MedDRA v23.1. The severity of all adverse events will be graded according to NCI CTCAE version 4.03.

A treatment-emergent adverse event (TEAE) is defined as an adverse event occurring on or after the first dose of study treatment and within 30 days after the last study treatment date.

TEAEs will be summarized by presenting, for each treatment arm, the count and percentage of patients having any TEAE, having a TEAE in each system organ class, and having an individual event according to version 23.1 of the MedDRA dictionary (or later as specified in the Data Management Plan). The version of MedDRA used for the purpose of coding events in the clinical database will be static for the duration of the study. CTCAE (version 4.03) grades and relationship to study drug will be summarized as appropriate. For summaries by CTCAE grade or relatedness, only the highest CTCAE grade or degree of relatedness of each

System Organ Class and/or preferred term (PT) will be summarized. A patient having the same event more than once will be counted only once and by greatest severity or closest relationship.

Cardiac TEAEs are all the PTs in the Standardised MedDRA Queries (SMQs) of Cardiac Arrhythmias, Cardiac Failure, Ischaemic Heart Disease, and Embolic and Thrombotic Events.

Haemorrhage TEAEs are all PTs in the SMQ of Haemorrhages.

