The majority of non-hematologic AEs was mild or moderate in severity, and rates were generally similar across dosing arms with the exception of gastrointestinal events, which occurred more commonly in patients treated at 200 mg BID (39/54, 72.2%) than in patients treated at lower doses (100 mg QD: 26/52, 50.0%; 100 mg BID: 30/55, 54.5%). These events were largely grade 1 or 2 and usually occurred within the first 8 weeks on treatment. Diarrhea was common but generally manageable with standard antidiarrheal agents and tended to be short-lived: the median duration of pacritinib-related diarrhea was 2 weeks. The most common hematologic AEs were thrombocytopenia and anemia, both of which occurred more frequently in patients treated at 200 mg BID (40.7% and 24.1% respectively). Cardiac events were more common in patients treated at 200 mg BID (40.7%, n = 22) than in patients treated at lower doses (100 mg QD: 21.2%, n = 11; 100 mg BID: 21.8%, n = 12) but were largely grade 1 or 2 in severity, with the most common being peripheral edema (200 mg BID: 16.7%) and QT prolongation (200 mg BID: 7.4%). There was no excess in grade 3 or 4 cardiac events in patients treated at the highest dose (100 mg QD: 5.8%, n = 3; 100 mg BID: 5.5%, n = 3; and 200 mg BID: 3.7%, n = 2; no grade 4 events). The mean change in corrected QT interval (QTc) between Baseline and Week 24 was roughly +10 msec on all arms; no patient had a QTc > 500 msec. Bleeding events were more common in patients treated at 200 mg BID (42.6%, n = 23) than in patients treated at lower doses (100 mg QD: 36.5%, n = 19; 100 mg BID: 25.5%, n = 14) but were largely grade 1 or 2 in severity, with the most common being epistaxis (200 mg BID: 14.8%) and bruising (200 mg BID: 9.3%). There was no excess in grade 3 or 4 bleeding events in patients treated at the highest dose (100 mg QD: 7.7%, n = 4; 100 mg BID: 3.6%, n = 2; and 200 mg BID: 5.6%, n = 3; no grade 4 events). The rate of fatal events was similar across all arms: 100 mg QD: 7.7%, n = 4 (sepsis, disease progression, tuberculosis, and general state deterioration); 100 mg BID: 5.5%, n = 3 (myelofibrosis, subdural hemorrhage, and heart failure); and 200 mg BID: 5.6%, n = 3 (sepsis, respiratory failure, and subdural hematoma).

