### 7.1 General Statistical Considerations

Unless specified otherwise, the analyses of data collected will be descriptive and summaries will be presented separately for each treatment arm and in total for the specified analysis population. Statistical analyses will be descriptive and no formal hypothesis testing or comparative analyses between treatment arms will be performed unless stated. Confidence intervals (CIs) will be constructed at the 95% confidence level where appropriate. For categorical variables, confidence intervals will be calculated using the Clopper-Pearson method where appropriate.

For continuous variables, the number of observations (n), mean, standard deviation, median, q1, q3, minimum, and maximum will be provided as summary statistics. For categorical variables, the frequency and percentage in each category will be displayed.

Summary tables will in general display 2 treatment arms:

- Pacritinib 400 mg
- Placebo

A total column will be added for table summaries if appropriate.

Efficacy analyses will in general be based on the ITT Population according to the randomized (planned) treatment arm.

Safety analyses will in general be performed using the Safety Population according to the treatment actually received.

Subject disposition, demographics, and clinical baseline characteristics data will be summarized for the ITT Population. If the ITT Population differs from other defined analysis populations, additional patient characteristic summaries may be generated using other analysis populations.

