### **7.5.1 Adverse Events**

Summaries of adverse events will be presented by treatment arm and in total for the Safety Population.

An overview of treatment-emergent adverse events will be provided which summarizes the patient incidence of the following for the Safety Population. This overview will include the number and percentage of patients with:

- Any TEAEs,
- TEAEs related to study treatment,
- Serious TEAEs (TESAEs),
- CTCAE Grade 3+ TEAEs,
- TEAEs with outcome of death,
- TEAEs leading to study drug discontinuation, interruption, or dose reduction,
- Cardiac TEAEs (defined by MedDRA SMQ List),

- Haemorrhage TEAEs (defined by MedDRA SMQ List),

The number and percentage of patients with TEAEs will be tabulated by the highest CTCAE Grade, System Organ Class, and Preferred Term (PT).

In addition, serious TEAEs (TESAEs), CTCAE grade 3 or more TEAEs, TEAEs leading to study drug discontinuation, interruption, or dose reduction, TEAEs with an outcome of death, and related TEAEs will be summarized by System Organ Class and PT.

The PT of TEAEs of all grades and grade 3 or more TEAEs will also be presented for each treatment arm in order of decreasing frequency.

Cardiac and haemorrhage TEAEs will also be summarized by System Organ Class and PT.

For all above summaries, patients with multiple adverse events will be counted only once per System Organ Class and PT.

Listings of all AEs (i.e. including those that are not treatment-emergent), SAEs, AEs leading to treatment discontinuation, AEs leading to treatment interruption or dose reduction, AEs with outcome of death, Cardiac TEAEs, and Haemorrhage TEAEs will be provided.

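### The SAP's Cardiac TEAE category includes every embolic and thrombotic term and is reported as one row, so neither a cardiac rate nor a thromboembolic rate is shown on its own

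*SAP*

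**What the plan says.** SAP 6.3.1 sets the rule: "Cardiac TEAEs are all the PTs in the Standardised MedDRA Queries (SMQs") of "Cardiac Arrhythmias, Cardiac Failure, Ischaemic Heart Disease, and Embolic and Thrombotic Events". It takes every preferred term in each query and does not restrict the fourth to cardiac terms. The only other special category is bleeding: "Haemorrhage TEAEs are all PTs in the SMQ of Haemorrhages".

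SAP 7.5.1 uses the category in three places. It is one of eight rows in the TEAE overview, "Cardiac TEAEs (defined by MedDRA SMQ List"). It is then tabulated ("Cardiac and haemorrhage TEAEs will also be summarized by System Organ Class and PT"), with each patient counted once per class and once per term. It is also listed by patient. No summary by individual query is planned.

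For safety data these are descriptive summaries. SAP 7.1 states that "no formal hypothesis testing or comparative analyses between treatment arms will be performed unless stated", and no test of adverse event rates is stated.

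The protocol's overview of PAC203, in section 1.2.4, explains why a cardiac rate is of interest: "Cardiac events were more common in patients treated at 200 mg BID (40.7%, n = 22) than in patients treated at lower doses". The lower-dose figures are 21.2% and 21.8%. The same text says that most of these events were grade 1 or 2 and that grade 3 or 4 cardiac events were not more frequent at the top dose.

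**The concern.** The toxicity profile is a secondary objective, and 200 mg BID is this trial's dose from Day 2. A reader who wants to know whether the PAC203 cardiac pattern recurs will look first at the cardiac row. That row answers a different question: how many patients had a cardiac event or an embolic or thrombotic event.

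Two things are lost from the prespecified output:

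- a patient-level rate for the three cardiac queries alone;
- a patient-level thromboembolic rate to set beside the haemorrhage rate. The protocol (6.5.2) associates the drug with thrombocytopenia and bleeding and ties anticoagulant use during study drug to the platelet count, so a reader would want to see bleeding and clotting together.

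Because adverse events are summarised descriptively, the percentages in these tables are the result. A label that does not match its contents is carried straight into the report.

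**Working it through.** **The plan's figures.** No number in the SAP depends on this definition. The PAC203 percentages reproduce from the protocol's counts: 22/54 = 40.7%, 11/52 = 21.2%, 12/55 = 21.8%. The two lower doses pooled give 23/107 = 21.5%.

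**What each planned output can show.**

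- Overview row: patients with any event in the four-query union. The components are not separated.
- System organ class and term table: patients counted once per class and once per term. A patient can appear in several rows, so rows cannot be added to give patients with any event in a query. A system organ class is also a different grouping from a query.
- Listings: the per-query counts can be rebuilt from them, but the plan does not ask for this.
- QTcF analysis (SAP 7.5.4): isolates QT prolongation only.

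**Size of the dilution.** The inputs are assumptions, because the documents give no thromboembolic rate. Let c be the proportion with a cardiac event and t the proportion with a thromboembolic event, independent within a patient.

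Union = 1 − (1 − c)(1 − t). With the same t in both arms, the difference in the union is (1 − t) times the cardiac difference.

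Cardiac 20% pacritinib v 10% placebo (difference 10 points, ratio 2.0), with t = 15% in both arms:

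- pacritinib: 1 − 0.80 × 0.85 = 32.0%
- placebo: 1 − 0.90 × 0.85 = 23.5%
- difference 8.5 points; ratio 0.320/0.235 = 1.36

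| t, both arms | Pacritinib | Placebo | Difference | Ratio |
|---|---|---|---|---|
| 5% | 24.0% | 14.5% | 9.5 | 1.66 |
| 10% | 28.0% | 19.0% | 9.0 | 1.47 |
| 15% | 32.0% | 23.5% | 8.5 | 1.36 |
| 20% | 36.0% | 28.0% | 8.0 | 1.29 |
| 30% | 44.0% | 37.0% | 7.0 | 1.19 |

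With 40.7% and 21.5% as assumed arm rates and t = 20% in both arms, the union is 1 − 0.593 × 0.80 = 52.6% v 1 − 0.785 × 0.80 = 37.2%. The difference falls from 19.2 to 15.4 points and the ratio from 1.89 to 1.41.

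**Dependence on independence.** Take c = 20% v 10% and t = 15% again. If no patient has both kinds of event, the union is the sum: 35% v 25%, a difference of 10 points and a ratio of 1.40. If overlap is as large as possible, the union is the larger of c and t: 20% v 15%, a difference of 5 points and a ratio of 1.33. So the difference lies between 5 and 10 points and the ratio between 1.33 and 1.40, with the same kind of overlap in both arms.

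**Unequal thromboembolic rates.** These are hypothetical in both directions, with cardiac 20% v 10% and independence.

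- t = 20% pacritinib v 10% placebo: 1 − 0.80 × 0.80 = 36% v 1 − 0.90 × 0.90 = 19%. The 10-point difference appears as 17.
- t = 10% pacritinib v 20% placebo: 1 − 0.80 × 0.90 = 28% v 1 − 0.90 × 0.80 = 28%. The difference appears as 0.

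**The case against.** The category is prespecified, fully defined and applied alike to both arms, and it contradicts nothing in the protocol, which defines no cardiac grouping. All of that stands. So do these points:

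- The planned tables do give patient counts without double counting, by system organ class and by term. It would be wrong to infer that no patient-level breakdown exists. What is missing is narrower: a count per query.
- A reader might infer that the toxicity objective rests on this blended number. It does not. SAP 6.3 assesses the objective through incidence, seriousness, relatedness and severity of all TEAEs, and the cardiac row is one of eight.
- QT prolongation, one of the two commonest cardiac events at 200 mg BID in PAC203, has its own analysis in SAP 7.5.4.
- No decision depends on the row. The between-arm safety trigger in protocol 8.4.1 and 15 uses grade 4 or 5 treatment-related events.
- The protocol does not say how PAC203 defined cardiac events. Peripheral edema was counted among them, so a three-query rate is not guaranteed to match PAC203 either.
- The documents do not list the terms in each query, so overlap between queries cannot be checked from them.

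The objection does not remove the mismatch between label and content. The listings allow a later split, but SAP section 1 would label that additional analysis post hoc, after results are known. If a broad composite is wanted, it can be kept under an accurate name.

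**Conclusion.** The point holds as a minor reporting matter. As written, the cardiac percentage does not isolate cardiac events, and no thromboembolic percentage stands beside the haemorrhage percentage. The remaining outputs separate the two only in part.

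Under independence, an equal thromboembolic rate of 15% turns a 10-point cardiac difference into 8.5 points and a ratio of 2.0 into 1.36. All the rates used here are assumptions. The loss in the difference depends on how far the two kinds of event overlap within patients; the ratio falls in every equal-rate case shown.

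A reader might go further and infer that a cardiac excess could be cancelled. The arithmetic allows it, but nothing in the documents indicates that thromboembolism falls on pacritinib; they give neither a rate nor a direction. At the PAC203 cardiac rates, full cancellation would need about 30% thromboembolism on placebo against 7% on pacritinib: 1 − 0.785 × 0.70 = 45.1% v 1 − 0.593 × 0.93 = 44.9%. It is a hypothetical, as is the opposite case, in which a thromboembolic excess would be read as a cardiac one.

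No sample size, error rate, endpoint or safety trigger is affected.

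**What to change.** In SAP 6.3.1, define Cardiac TEAEs by the Cardiac Arrhythmias, Cardiac Failure and Ischaemic Heart Disease queries, and make Embolic and Thrombotic Events a category of its own. In SAP 7.5.1, give the new category its own overview row, class-and-term table and listing, and add patient counts per query by arm. State that a patient may count under more than one query. The four-query composite may stay as an extra row if its label says what it contains.

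The cost is a sentence or two of SAP text, one overview row, one table and one listing. The events are already to be coded in MedDRA, so no new data are needed.

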## 7 STATISTICAL ANALYSES

This section describes the statistical analyses to be conducted in relation to the primary, secondary, and exploratory objectives of the study.

### 7.1 General Statistical Considerations

Unless specified otherwise, the analyses of data collected will be descriptive and summaries will be presented separately for each treatment arm and in total for the specified analysis population. Statistical analyses will be descriptive and no formal hypothesis testing or comparative analyses between treatment arms will be performed unless stated. Confidence intervals (CIs) will be constructed at the 95% confidence level where appropriate. For categorical variables, confidence intervals will be calculated using the Clopper-Pearson method where appropriate.

For continuous variables, the number of observations (n), mean, standard deviation, median, q1, q3, minimum, and maximum will be provided as summary statistics. For categorical variables, the frequency and percentage in each category will be displayed.

Summary tables will in general display 2 treatment arms:

- Pacritinib 400 mg
- Placebo

A total column will be added for table summaries if appropriate.

Efficacy analyses will in general be based on the ITT Population according to the randomized (planned) treatment arm.

Safety analyses will in general be performed using the Safety Population according to the treatment actually received.

Subject disposition, demographics, and clinical baseline characteristics data will be summarized for the ITT Population. If the ITT Population differs from other defined analysis populations, additional patient characteristic summaries may be generated using other analysis populations.

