## **8.4 Safety Surveillance**

### ***8.4.1 Routine Pharmacovigilance Monitoring***

The Sponsor will monitor safety data during the clinical study by examining the incidence and severity of AEs and changes in laboratory results. Clinically important increases in the rate of serious adverse reactions will be communicated to the IDMC (see Section 2.2), investigators, and

regulatory agencies, as appropriate. A clinically important increase will be considered an increase in frequency and/or severity in an event that leads to a serious outcome and exceeds the rate(s) of the reported event listed in the Investigator Brochure reference safety information. In addition, if the sponsor observes a difference of  $> 6\%$  in the frequency (and a difference of  $\geq 2$  patients between the 2 arms) of grade 4 or 5 treatment-related AEs in the pacritinib arm compared to the placebo + SOC arm, the IDMC will be convened to review the risk profile and render a recommendation regarding study continuation. The FDA and other Competent Authorities will be notified of any IDMC meeting that is convened under these circumstances, and the resultant decision will be reported to the FDA within 2 business days.

Single events assessed as serious, unexpected, and related will continue to be reported on an expedited basis per regulatory requirement.

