### 2.2 Secondary Objectives

1. To compare the number of ventilator-free days, defined as the number of days that patients are alive and not intubated, from randomization to Day 28 between pacritinib + SOC versus placebo + SOC
2. To compare the mortality rate between pacritinib + SOC versus placebo + SOC at Day 28
3. To compare the mortality rate between pacritinib + SOC versus placebo + SOC at Day 15
4. To compare the time to improvement by at least 2 points relative to Baseline on the 7-point ordinal scale of clinical status between pacritinib + SOC versus placebo + SOC
5. To compare the clinical status assessed by the 7-point ordinal scale of clinical status at Days 8, 15, 22, and 28 between pacritinib + SOC versus placebo + SOC
6. To compare the rate of use of immunomodulatory agents as treatment for COVID-19 during the 28 days following randomization between pacritinib + SOC versus placebo + SOC
7. To evaluate the toxicity profile of pacritinib therapy in hospitalized patients with severe COVID-19 with or without cancer

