## **7.5 Safety Analyses**

Safety will be assessed through 30 days of follow-up after the last dose of study treatment and assessed by the cumulative incidence, severity and seriousness of TEAEs, drug discontinuations, laboratory values, and clinical assessments.

Summaries will be tabulated by treatment arm and in total for the Safety Population.

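### Adverse events are planned as counts and percentages by arm, with no estimate of the difference from placebo and no precision for it

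*SAP*

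**What the plan says.** - **Default rule.** SAP 7.1 makes analyses descriptive: "no formal hypothesis testing or comparative analyses between treatment arms will be performed unless stated".
- **Intervals.** The same section adds "Confidence intervals (CIs) will be constructed at the 95% confidence level where appropriate" and "For categorical variables, confidence intervals will be calculated using the Clopper-Pearson method where appropriate". Clopper-Pearson gives an interval for one proportion, so it applies within an arm.
- **Adverse events.** SAP 7.5 says "Summaries will be tabulated by treatment arm and in total for the Safety Population". SAP 7.5.1 introduces its main table with "This overview will include the number and percentage of patients with" and lists any, related, serious, Grade 3+, fatal, treatment-modifying, cardiac and haemorrhage TEAEs. No difference, ratio or interval is named there or in SAP 6.3.1. Protocol 11.4 is also limited to number and percentage by arm.
- **Objective.** Secondary objective 7 is "To evaluate the toxicity profile of pacritinib therapy in hospitalized patients with severe COVID-19 with or without cancer". Objectives 1 to 6 each ask for a comparison.
- **Contrast with efficacy.** SAP 7.4.1, 7.4.2.2 and 7.4.2.5 call for a difference in rates with a 95% interval for the primary endpoint, mortality and immunomodulatory agent use.
- **Monitoring trigger.** Protocol 8.4.1 and 15 convene the IDMC if the sponsor observes a difference above 6%, and of at least 2 patients, in the frequency "of grade 4 or 5 treatment-related AEs in the pacritinib arm compared to the placebo + SOC arm".

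**The concern.** Patients with severe COVID-19 will have serious events in both arms whatever they receive. Protocol 1.1.1 puts mortality among hospitalized patients at about 25%. What pacritinib adds can be seen only as a difference from placebo, and that is the quantity the safety tables leave out.

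Cardiac and haemorrhage events are the two groups the SAP singles out, and in PAC203 both were more frequent at 200 mg BID than at lower doses (Protocol 1.2.4). If the report shows two similar percentages and nothing else, a reader may take them as evidence of no excess. If it shows one percentage twice the other, a reader may take that as harm. At this sample size neither reading may be supported. Protocol 1.2.4 already uses the first kind of statement about small counts: "There was no excess in grade 3 or 4 bleeding events in patients treated at the highest dose".

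**Working it through.** **1. Arm size.** The plan gives no precision figure for safety, so its own figure here is the sample size: about 200 patients, 1:1, for 26.5% against 13.5%, one-sided 0.10, 80% power (SAP 3.4).

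- Uncorrected: n = [1.2816·√(2·0.20·0.80) + 0.8416·√(0.265·0.735 + 0.135·0.865)]² / 0.13² = (0.725 + 0.470)² / 0.0169, about 84.5, so 85 per arm.
- With the continuity correction: (84.5/4)·[1 + √(1 + 4/(84.5·0.13))]², about 99.3, so 100 per arm.

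The stated 200 reproduces with the correction. I take 100 dosed patients per arm. This is an assumption, because the documents give no non-dosing rate.

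**2. Method.** Newcombe's interval for p1 − p2 uses the Wilson limits (l, u) of each arm:

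- (l, u) = [p + z²/2n ± z·√(p(1−p)/n + z²/4n²)] / (1 + z²/n), with z = 1.96
- lower = (p1 − p2) − √[(p1 − l1)² + (u2 − p2)²]
- upper = (p1 − p2) + √[(u1 − p1)² + (p2 − l2)²]

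Example, 5/100 in each arm: the Wilson limits are 2.15% and 11.18%, so the upper limit is √(6.18² + 2.85²) = 6.8 points.

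**3. Equal observed rates, 100 per arm.** The rates are assumed.

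| Rate in each arm | 95% interval for the difference (points) |
|---|---|
| 2% | ±5.2 |
| 3% | ±5.8 |
| 4% | ±6.3 |
| 5% | ±6.8 |
| 8% | ±8.0 |
| 10% | ±8.7 |
| 20% | ±11.1 |
| 41% | ±13.4 |

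The last row is close to the PAC203 any-grade rates at 200 mg BID: bleeding 42.6% (23/54) and cardiac 40.7% (22/54). With 90 per arm the half-widths are 6.2 at 3%, 7.2 at 5% and 14.0 at 40%.

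**4. An apparent doubling.** 10/100 against 5/100 is +5 points, with an interval of −2.6 to +13.0.

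**5. The 6-point figure as a yardstick.** With 100 per arm, equal rates exclude a 6-point excess at 3% per arm (upper limit 5.8) but not at 4% (6.3). With 90 per arm they exclude it at 2% (5.6) but not at 3% (6.2).

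**6. The PAC203 grade 3 or 4 bleeding counts.**

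- 3/54 against 2/55: 5.6% − 3.6% = +1.9 points before rounding, interval −7.5 to +11.8.
- 3/54 against 4/52: 5.6% − 7.7% = −2.1 points, interval −13.2 to +8.5.

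The two comparisons point in opposite directions, and both intervals include excesses above 8 points.

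**7. Per-arm intervals are not enough.** The Clopper-Pearson interval for 5/100 is 1.6% to 11.3%. Two such intervals side by side do not give the interval for the difference.

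Miettinen-Nurminen limits for the 3%, 4%, 5%, 8% and 41% rows and for steps 4 and 6 differ from these by less than 0.3 points.

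**The case against.** The strongest reply is that nothing here is inconsistent. Objective 7 alone says evaluate where the others say compare. Protocol 11.4 is descriptive and the SAP follows it. Descriptive reporting is a coherent choice for a Phase 2 trial sized on efficacy. The counts are given by arm, so anyone can compute the difference later, and safety during the trial rests on an IDMC with unblinded data. All of this stands. It limits the point to the precision of the final report.

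Four stronger readings are tempting, and the documents do not support them:

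- **That the SAP forbids safety comparisons.** Section 7.1 is a default with an exception that 7.5.1 leaves unused. Intervals are allowed where appropriate, and SAP 1 allows additional analyses labelled post hoc.
- **That bleeding, cardiac or serious event counts fall short of an alarm the protocol sets for them.** The trigger covers only grade 4 or 5 treatment-related events. It acts on the observed difference and is not a margin for a confidence limit. For other events, 6 points is only illustrative.
- **That equal counts can never be reassuring.** At 3% or less with 100 per arm they do exclude 6 points.
- **That the sponsor plans to read equal percentages as safe.** No text says so. The PAC203 sentence is background on a different study, and the same paragraph reports that bleeding and cardiac events of any grade were more common at 200 mg BID.

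**Conclusion.** The concern holds as a gap in precision. For secondary objective 7 the plan provides number and percentage by arm and no between-arm estimate, while mortality and immunomodulatory agent use receive a difference with a 95% interval.

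The size depends on the event rate, which the documents do not give for this population. The uncertainty that equal percentages would hide runs from about ±5 points for events at 2% to about ±13 points for events near 40%. Similar percentages should therefore not be reported as no excess, except for rare events. The conclusion rests on 100 dosed patients per arm, and slightly fewer patients widen every interval.

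The primary result, the analysis populations and the error rate are unaffected. The change is a worthwhile low-cost improvement, not the correction of an error.

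**What to change.** In SAP 7.5.1, as a stated exception to the default in 7.1:

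1. Add the pacritinib-minus-placebo risk difference with a 95% score interval (Newcombe or Miettinen-Nurminen) to the TEAE overview, at least for the serious, Grade 3+, fatal, cardiac and haemorrhage rows.
2. Add a row for grade 4 or 5 treatment-related TEAEs. The overview lists related and Grade 3+ events separately, so the category used by the IDMC trigger has no row of its own.
3. Give no p-values. Label the intervals as unadjusted estimation, and state that similar percentages are not evidence of no excess.

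The cost is one column, one row and a footnote. The drawback is several unadjusted intervals, some of which may exclude zero by chance, so the label matters.
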